4.2.2 Secondary Efficacy Endpoint

4.2.2.1 Duration of Response (DoR) by IRC

DoR will be derived from those patients who had a BOR of confirmed CR or PR only.

DoR by IRC is defined as the time from the date of first documented response, which is subsequently confirmed, until the date of documented progression or death (by any cause in the absence of progression). Documented response and progression are both identified based on the IRC evaluation. If a patient has not progressed or died at the cut-off for analysis, his/her duration of response will be consored at the last evaluable RECIST assessment.

The end of response should coincide with the date of progression or death from any cause used for the PFS endpoint (including primary analysis and sensitivity analysis, see more details in Section 4.2.2.2).

The algorithm for DoR is provided below:

DoR (months) = $\frac{\text{date of event/censoring} - \text{date of first response} + 1}{30.4375}$.

The rules for determination of response or progression date are described in Section 7.3.

4.2.2.2 Progression-Free Survival (PFS) by IRC

PFS by IRC is defined as the time from first dose of DZD9008 until the date of objective disease progression as defined by RECIST 1.1 based on IRC evaluation or death (by any cause in the absence of progression), regardless of whether the subject discontinues the study treatments or receives another anti-cancer therapy prior to progression.

Symptomatic deterioration will not be regarded as a progression event in this study.

For PFS primary analysis, PFS will be derived following the rules below: Patients who have not progressed or died at the cut-off for analysis will be censored at the time of the latest date of assessment from their last evaluable RECIST assessment. If the patient progresses or dies after two or more consecutively missed RECIST assessments visits, the patient will be censored at the latest evaluable RECIST assessment before the missed visit. If the patient has no evaluable visits post-baseline or does not have baseline data they will be censored on the first dose date unless they die within two RECIST assessment visits after baseline. If a patient discontinues treatment prior to progression and/or receives a new anticancer therapy prior to progression then these patients will continue to be followed until evidence of objective disease progression as defined by RECIST 1.1 and their PFS time will be derived as defined above.

Sensitivity analysis will be performed to handle the missing data with alternative methods. e.g.: If the patient progresses or dies after two or more consecutively missed RECIST assessments visits, the patient will be considered as event on the date of first radiological progression or death. More censoring rules for PFS are presented in Table 2.

The PFS will be calculated as:

PFS (months) = $\frac{\text{date of event/censoring -first dose date of DZD9008+1}}{30.4375}$.

Table 2 Censoring Rules for PFS Analyses

No.	Scenarios	PFS Primary Analysis	Sensitivity Analysis
1.1	No baseline or any post-baseline tumor assessments and without death during study	Censored/ Date of first dose	Same as primary analysis
1.2	No baseline or any post-baseline tumor assessments, but died after two tumor assessment visits (13 weeks) from date of the first dose.	Censored/ Date of first dose	Event/Date of Death
2	Progression documented between scheduled visits	Event/ Date of first radiological PD	Same as primary analysis
3	No progression at the time of data cut-off/discontinuation from the study	Censored/ Date of last visit with evaluable* radiological tumor assessment prior to data cut-off or discontinuation from the study.	Same as primary analysis
4	Treatment discontinuation for reason other than radiological PD	Data after discontinuation of treatment will be included when determining the time to progression	Same as primary analysis
5	New anticancer treatment started	Data after new anticancer treatment will be included when determining the time to progression	Same as primary analysis
6	Death between scheduled tumor assessment visits	Event/ Date of death	Same as primary analysis
7	Death or progression after two or more missed tumor assessment visit**	Censored/Date of last evaluable* radiological tumor assessment with documented non-progression	Event/Date of first radiological progression or death
8	No baseline or any post-baseline tumor assessments and died within two tumor assessment visits (13 weeks) from date of first dose	Event/Date of death	Same as primary analysis

^{*}Evaluable tumor assessment is a radiologic assessment of CR, PR, SD, non-CR/non-PD or PD.

^{**}Interval between the death/progression and the last evaluable tumor assessment before missed visits is longer than 14 weeks (98 days).

4.2.2.3 Disease Control Rate (DCR) by IRC

DCR by IRC is defined as the proportion of patients with a BOR of CR, PR or SD, based on the IRC evaluation. Details about BOR derivation (where confirmation of response is required or not) can be found in Section 4.2.1.

4.2.2.4 Percentage Change in Tumor Size by IRC

Tumor size by IRC is defined as the sum of the longest diameters (or short diameter for lymph nodes) of the target lesions identified by IRC according to RECIST 1.1. Percentage change in tumor size will be calculated for patients with measurable disease at baseline as below:

Percentage change from baseline (%)= tumor size at post-baseline visit – tumor size at baseline)/tumor size at baseline*100%.

Best change from baseline in percentage will also be identified based on the smallest tumor size post baseline. Only changes up to progression and before the start of new anticancer therapy will be considered for best change.

If best percentage change cannot be calculated due to missing data in tumor size, a value of 20% increase will be imputed as the best percentage change from baseline in the following situations (otherwise best percentage change will be left as missing):

- If a patient has died;
- If a patient has objective PD documented;
- If a patient discontinued treatment due to PD.

4.2.2.5 Endpoints by Investigators

In addition to the primary and secondary efficacy endpoints described above, the same set of endpoints (ORR, DoR, PFS, DCR and tumor size change) assessed by investigators will also be regarded as secondary endpoints.

The similar definition and derivations described above are also applicable for the endpoints assessed by investigators. The derivation will be made based on the visit overall response assessed by investigator.

4.2.2.6 Overall Survival (OS)

Following disease progression, the patient, patient's family, or the patient's current physician must be contacted every 3 months for survival information up to the time of the final OS analysis.

Overall survival is defined as the interval between the date of first dose and the date of patient death due to any cause. Patients who have not died at the cut-off for analysis will be censored at the time they were last known to be alive.

OS will be calculated as:

OS (months) = $\frac{\text{date of event/censoring -first dose date of DZD9008+1}}{30.4375}$.

4.2.3 Exploratory Efficacy Endpoint

In addition to the primary and secondary efficacy endpoint defined in CSP, time to response (TTR) will be derived for patients who achieved confirmed CR or PR in order to describe the onset of drug action.

TTR is defined as the time (days) from the first dose date of DZD9008 to the first documented response, which is subsequently confirmed. In addition, the visit at which the patient achieved the first response will also be identified.

4.3 Safety

4.3.1 Adverse Events (AE)

All AEs recorded on the CRF will be coded using the Medical Dictionary for Regulatory Activities (MedDRA) dictionary Version 25.0 (or a later version if updated during the study). Assessment of AE grade will be based on the National Cancer Institute-Common Terminology Criteria for Adverse Events (NCI-CTCAE, version 5.0).

The treatment-emergent AEs (TEAEs) are defined as the events meeting any of the criteria below: any event starting or worsening (in severity or seriousness) on or after the date of first dose of treatment (DZD9008) and up to 28 days after date of last dose of treatment; any events considered as related or with unknown/missing relationship to treatment.

If an event cannot be classified as TEAE or not after applying imputation rules for missing/incomplete dates (see Section 7.2), it will be considered as TEAE in analysis.

A treatment-related AE is an AE considered as 'related' or with unknown/missing relationship to treatment.

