6.4.3 Recording of adverse events

6.4.3.1 Time period for collection of adverse events

AEs will be collected from the first dosing of DZD9008 until the end of the follow-up period. SAEs will be collected from ICF sign. From the phase 1 data, terminal half-life of DZD9008 in human is around 50 hours. The safety follow-up duration would like to cover at least 5 folds of half-life to ensure the safety monitoring until elimination of DZD9008, Thus, the follow-up period is defined as 28 days after study treatment is discontinued.

SAEs occurring in the follow-up period should be reported to Dizal in the usual manner (see Section 6.4.4).

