7.9.3 Safety

All patients who receive at least one dose of DZD9008 will be included in the assessment of the safety profile (safety analysis set). At the end of the study, appropriate summaries of safety data will be produced, as defined below.

Data from all cycles of initial treatment will be combined in the presentation of safety data. AEs will be listed individually by patient and dose group. For patients who have a dose modification, all AEs (due to drug or otherwise) will be assigned to the initial dose group. The number of patients experiencing each AE will be summarized by the Medical Dictionary for Regulatory

Date: July 24,2023

Activities (MedDRA) system organ class, MedDRA preferred term and CTCAE grade. The number and percentage of patients with adverse events in different categories (eg, causally related, CTCAE grade \geq 3 etc) will be summarized by dose group in Part A and by dose cohort in Part B, and events in each category will be further summarized by MedDRA system organ class and preferred term, by dose group. SAEs will be summarized separately if a sufficient number occur.

Any AE occurring within the defined 28-day follow-up period after discontinuation of investigational product will be included in the AE summaries. Any adverse events in this period that occur after a patient has received further therapy for cancer (following discontinuation of investigational product) will be flagged in the data listings. AEs occurring after the 28 day follow-up period after discontinuation of investigational product will be listed separately, but not included in the summaries.

Hematology, clinical chemistry, vital signs and ECG data will be listed individually by patient and suitably summarized. For all laboratory variables, which are included in CTCAE 5.0, the CTCAE grade will be calculated. Summary statistics such as mean, median, standard deviation, minimum, maximum and number of observations will be used for continuous variables, frequency and percentages will be used for categorical variables.

Details of any deaths will be listed for all patients.

Any qualitative assessments will be summarized using the number and proportion of patients with results of negative, trace or positive.

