5.7 Safety

5.7.1 Adverse Event

Summary tables of AEs by treatment group and overall will be produced in the safety set. Only the TEAEs will be included in the summaries.

An overview table will be created to present the number and percentage of patients with at least one of the following TEAEs, where patients with more than one TEAE in a particular category will be counted only once in that category.

- any TEAE;
- drug-related TEAE;
- TEAE grade 3 or higher;
- drug-related TEAE grade 3 or higher;

- Treatment-emergent SAE;
- drug-related SAE;
- TEAE leading to drug interruption;
- drug-related TEAE leading to drug interruption;
- TEAE leading to dose reduction;
- drug-related TEAE leading to dose reduction;
- TEAE leading to drug discontinuation;
- drug-related TEAE leading to drug discontinuation;
- TEAE with fatal outcome;
- drug-related TEAE with fatal outcome;

The number and percentage of patients reporting each TEAE will be summarized by MedDRA System Organ Class (SOC) and/or Preferred Term (PT). The following summaries will be produced:

- TEAEs, by SOC and PT;
- drug-related TEAEs, by SOC and PT;
- TEAEs of Grade 3 or higher, by SOC and PT;
- drug-related TEAEs of Grade 3 or higher, by SOC and PT;
- TEAEs, by SOC, PT and maximum CTCAE grade;
- drug-related TEAEs, by SOC, PT and maximum CTCAE grade;
- Treatment-emergent SAEs, by SOC and PT;
- drug-related treatment-emergent SAEs, by SOC and PT;
- TEAEs leading to drug interruption, by SOC and PT;
- drug-related TEAEs leading to drug interruption, by SOC and PT;
- TEAEs leading to dose reduction, by SOC and PT;

drug-related TEAEs leading to dose reduction, by SOC and PT;

- TEAEs leading to drug discontinuation, by SOC and PT;
- drug-related TEAEs leading to drug discontinuation, by SOC and PT;
- TEAEs with fatal outcome, by SOC and PT;
- drug-related TEAEs with fatal outcome, by SOC and PT;

Additional tables for common TEAEs may be provided to facilitate the CSR development.

In the above summaries, patients with more than one AE within a particular SOC are counted only once for that SOC. Similarly, patients with more than one AE within a particular PT are counted only once for that PT.

For summaries by maximum severity, patients with multiple AEs within a particular SOC or PT will be counted under the category of their most severe AE within that SOC or PT. If CTCAE grade is missing for a TEAE, it will be counted as missing category in the summary tables by maximum grade.

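### The SAP's second TEAE criterion has no date limit: late events that are related or lack causality enter the AE summaries against Protocol 7.9.3, and a pre-dose SAE with missing causality would count as drug-related

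*SAP*

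**What the plan says.** SAP 4.3.1 joins two criteria as alternatives: TEAEs "are defined as the events meeting any of the criteria below". The first is dated. It needs onset or worsening "on or after the date of first dose of treatment (DZD9008) and up to 28 days after date of last dose of treatment". The second has no start or end date: "any events considered as related or with unknown/missing relationship to treatment". The same section adds two defaults. An event that still cannot be classified after date imputation is a TEAE, and unknown or missing causality is counted as treatment-related.

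SAP 5.7.1 makes TEAE status the only entry condition for the AE tables: "Only the TEAEs will be included in the summaries".

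Protocol 7.9.3 divides events by time alone. On one side, "Any AE occurring within the defined 28-day follow-up period after discontinuation of investigational product will be included in the AE summaries". On the other, "AEs occurring after the 28 day follow-up period after discontinuation of investigational product will be listed separately, but not included in the summaries". It makes no exception for related events. Protocol 6.4.3.1 fixes the boundary ("the follow-up period is defined as 28 days after study treatment is discontinued") and sets the start of collection: AEs from first dose, but "SAEs will be collected from ICF sign".

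**The concern.** A definition of treatment-emergent normally rests on timing, with causality handled afterwards. Here causality alone is enough, whatever the onset date. That has two consequences.

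- **After 28 days.** The SAP summarises some events that the protocol says are only to be listed. Two programmers, one working from each document, would produce different AE tables.
- **Before the first dose.** A serious event that began before any drug was taken can be tabulated as treatment-emergent and, through the missing-causality default, as drug-related.

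At stake is the accuracy of the serious, fatal and drug-related rows in Part B, the part planned to support an NDA submission. In those rows a single patient is visible.

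**Working it through.** There is no sample-size or error-rate figure to reproduce. The check applies the SAP rule to each kind of event and sets the result beside Protocol 7.9.3.

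**Rule (SAP 4.3.1).** TEAE = A or B, where A = onset or worsening from first dose to last dose + 28 days, and B = causality related, unknown or missing. The protocol counts its 28 days from discontinuation and the SAP from last dose. I treat these as the same day.

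| Event | A | B | Status under the SAP | Protocol 7.9.3 |
|---|---|---|---|---|
| 1. Starts or worsens in the window, any causality | yes | either | TEAE, summarised | Summarised |
| 2. Starts after 28 days; related, unknown or missing | no | yes | TEAE, summarised as drug-related | Listed separately, not summarised |
| 3. Starts after 28 days; recorded as unrelated | no | no | Not a TEAE | Agrees |
| 4. SAE before first dose, causality missing, no later worsening, patient then dosed | no | yes | TEAE, summarised as drug-related | No rule stated |
| 5. SAE before first dose, recorded as unrelated, no later worsening | no | no | Not a TEAE | No rule stated |

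**What B adds.** Any event in the window is already a TEAE through A, and events that cannot be classified are caught by the separate default. So the only datable events that B can add are those in rows 2 and 4.

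**Does another section limit B?** SAP 7.2 imputes dates but puts no time condition on B. SAP 5.7.1 lists all AEs together with a treatment-emergence flag, and events in rows 2 and 4 would carry that flag.

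**Can such events arise?**

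- Row 2: Protocol 6.3.6.1 restricts collection beyond 28 days to ongoing AEs and procedure-related SAEs. Protocol 6.4.3.2 has the sponsor notified of suspected drug-related SAEs at any time after a patient completes the study, and Protocol 6.4.4 has all SAEs entered in the CRF. A procedure-related SAE falls in row 2 only if its relationship to the drug is recorded as related or left missing.
- Row 4: only SAEs can reach it, because non-serious AEs are collected from first dose. The patient must also be dosed, since the safety set in SAP 3.3 requires one dose.

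**Size.** Neither document gives an event count. With the planned 103 patients in an arm, one extra patient moves an incidence by 1/103 = 0.0097, or about 1 percentage point. A smaller treated arm would move by more.

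**The case against.** The best defence is that the clause is deliberately cautious and nearly empty in practice. SAP 4.3.1 resolves every doubt towards counting harm, and keeping late related events fits that pattern; any error over-reports toxicity. Causality is a yes/no question for each AE (Protocol 6.4.3.2). The causality guide in Appendix B asks whether the patient actually received the drug, which points to no for a pre-dose event. Missing data are queried (Appendix E), and little is collected after 28 days. All AEs remain in the listing, and SAP 5.7.1 plans, if data allow, to summarise deaths by period split at 28 days after last dose.

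Most of this stands as a limit on size. It does not remove the conflict. The SAP nowhere says that it departs from Protocol 7.9.3 on purpose. Caution cannot make a pre-dose event that never worsens treatment-emergent. Cautious handling of missing causality is already secured by the separate treatment-related definition. The listing helps only a reader who checks dates, because the flag itself would be wrong.

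Four stronger readings are tempting and are not supported:

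- A reader might infer that every safety table is affected. Laboratory, vital-sign, ECG, ECOG and cardiac or lung-function summaries (SAP 5.7.2 to 5.7.6) do not use TEAE status, and worst-case summaries have their own 28-day window (SAP 7.1).
- A reader might infer that the pre-dose part breaches the protocol. The protocol neither defines a TEAE nor excludes pre-dose SAEs from summaries.
- A reader might infer that all late events are swept in. Those recorded as unrelated stay out (row 3).
- A reader might infer that the SAP judges pre-dose events to be caused by the drug. It applies a default to missing data.

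**Conclusion.** The point holds in a narrow form. For events starting more than 28 days after last dose that are related or lack causality, the SAP and Protocol 7.9.3 give opposite instructions, and no other section settles which applies. The inclusion of pre-dose SAEs with missing causality is a separate defect internal to the SAP definition.

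The effect is confined to the AE summary tables and is probably a few events at most. That is a judgement from the collection rules, since no counts are available. It touches no efficacy result, test or dose decision. It could matter only in sparse rows, where one patient in 103 is about 1 percentage point. This is a minor correction, worth making because the rule as written misclassifies events and costs almost nothing to put right.

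**What to change.** In SAP 4.3.1, confine the second criterion to events starting or worsening on or after first dose and no later than 28 days after last dose. So bounded, it adds nothing to the first criterion, and deleting it would have the same effect. Use unknown or missing causality only to classify the relatedness of events that are already TEAEs. List events after 28 days separately, as Protocol 7.9.3 requires.

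If the sponsor wants late related events summarised, show them in a separate row outside the TEAE counts and amend Protocol 7.9.3 to say so. The first-dose condition is needed under either choice.

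The cost is one sentence in the SAP, a matching change to the TEAE flag, and one protocol sentence if late related events are kept. No new data are needed.

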4.3.2 Laboratory Data

Data for the serum chemistry, hematology, coagulation and urinalysis analytes will be collected as scheduled in the protocol, through local laboratory.

Serum Chemistry	Hematology	Coagulation	Urinalysis
Serum (S)/Plasma (P)- Albumin	Blood (B)-Hemoglobin	APTT	U-Glucose
S/P-Alkaline phosphatase	B-Hematocrit	INR	U-Protein
S/P-ALT	B-Platelet count		U-Blood
S/P-AST	B-Reticulocyte		
S/P-Bicarbonate	B-Red blood cell count		
S/P-Urea nitrogen	B-White blood cell count		
S/P-Calcium	B-Absolute leukocyte		
S/P-Creatinine	differential cell count:		
S/P-Glucose	Basophils		
	Eosinophils		

Serum Chemistry	Hematology	Coagulation	Urinalysis
S/P-Potassium	• Lymphocytes		
S/P-Magnesium	• Monocytes		
S/P-Sodium	Neutrophils		
S/P-Total bilirubin			
S/P-Total serum protein			
S/P-Lipase			
S/P-Amylase			
S/P-Creatine phosphokinase			

Additional urine/serum samples will be collected from all females of childbearing potential at screening before first dose, and at treatment discontinuation for a pregnancy test.

All laboratory data will be converted to International System of Units (SI) for analysis purpose. All values will be checked against the reference range (if available) and values out of reference range will be flagged as high or low (or abnormal for urinalysis data).

For analysis purposes, values preceded by a '<' or a '>' sign (i.e. those below or above the limits of quantification) will be multiplied by 0.5 and 1.5, respectively.

The CTCAE grade will be assigned for the laboratory tests applicable, following the criteria in NCI-CTCAE version 5.0. Data not meeting the existing criteria will be assigned as grade 0. The detailed criteria are shown in Appendix B.

To examine the abnormality in liver function tests (including potential Hy's law cases), patients meeting the criteria in Appendix C from first dose of DZD90008 until 28 days post last dose will be identified for further analysis.

